5.9 Subject Withdrawal, Replacement and Criteria for Early Trial Termination

5.9.1 Subject Withdrawal/Discontinuation Criteria

Subjects may withdraw consent at any time for any reason or be dropped from the trial at the discretion of the investigator should any untoward effect occur. In addition, a subject may be withdrawn by the Investigator if enrollment into the trial is inappropriate, the trial plan is violated, or for administrative and/or other safety reasons. Specific details regarding discontinuation or withdrawal are provided in Section 7.1.4 – Other Procedures.

A subject must be discontinued from the trial treatment for any of the following reasons:

- The subject withdraws consent.
- Confirmed radiographic disease progression. See Section 7.1.2.6
- Unacceptable adverse events as described in Section 5.4.2
- Intercurrent illness that prevents further administration of treatment
- Investigator's decision to withdraw the subject
- The subject has a confirmed positive serum pregnancy test
- Noncompliance with trial treatment or procedure requirements
- The subject is lost to follow-up

- Completed 24 months of treatment with pembrolizumab
 - Note: 24 months (104 weeks) of study medication is calculated from the date of first dose. Subjects who stop pembrolizumab after 24 months may be eligible for up to 12 months of additional study treatment if they progress after stopping study treatment provided they meet the requirements detailed in Section 7.1.5.2.1.
- Administrative reasons

The End of Treatment and Follow-up visit procedures are listed in Section 6 (Protocol Flow Chart) and Section 7.1.5 (Visit Requirements). After the end of treatment, each subject will be followed for 30 days for adverse event monitoring (serious adverse events will be collected for 90 days after the end of treatment as described in Section 7.2.3.1). Subjects who discontinue for reasons other than progressive disease will have post-treatment follow-up for disease status until disease progression, initiating a non-study cancer treatment, withdrawing consent or becoming lost to follow-up. After documented disease progression, each subject will be followed by telephone for overall survival until death, withdrawal of consent, or the end of the study, whichever occurs first.

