6. Prior to radiation therapy a dental evaluation will be done if recommended by treating radiation oncologist. Extraction of extensively diseased teeth should be carried out with conservation of restorable teeth where possible. At least 10 days should be allowed for healing of gingivae post-extraction. Because dental evaluation would be required for reirradiation as part of standard of care this evaluation/treatment can begin before consent for the trial.
7. For women of reproductive potential, a urine pregnancy test will be performed within 72 hours prior to first dosage of pembrolizumab. If a urine pregnancy result can't be confirmed as negative, then a serum pregnancy test will be required. Pregnancy testing may be repeated if pregnancy is suspected.
8. CBC to include white blood cells, hgb/hct, platelets and differential. CBC as part of screening for organ function (inclusion criteria # 13) is required to be done within 21 days of start date
9. Tumor imaging will determine the subsequent study treatment plan. Definition of response is detailed in section 7.1.2.6. Subjects with a complete response (CR), partial response (PR), and progressive disease (PD) will require confirmation by repeat CT scan. Subjects will remain on pembrolizumab following section 6.3 until response confirmation. Subjects with confirmed CR will follow Chart 6.2. Subjects with confirmed partial response **or who have** stable disease will **continue** to follow Chart 6.3. Subjects with confirmed progressive disease will follow Chart 6.4. See section 7.1.2.6 for all details on definitions of response.
10. Provide adequate tissue (core or incisional/excisional biopsy) prior to starting study treatment. This tissue will be used for PD-L1 analysis. Fresh tissue or archival tissue sample can only be used. If adequate tissue cannot be safely obtained than the patient may still be able to be enrolled on the trial after discussion with the study principal investigator, as long as FNA was done to confirm recurrent/second primary HNSCC. If the subject signs the Future Biomedical Research (FBR) consent, any leftover tissue that would ordinarily be discarded at the end of the main study will be retained for FBR.
11. Patient Reported Outcome Measures will be completed by the patient. The EORTC QLQ C-30 should be completed first.
12. Coagulation studies will be repeated as clinically necessary.

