Concomitant Medication Review	X	X	X	X	X	X	X	X	X		
Laboratory Procedures/Assessments											
CBC with Differential	X	X	X	X	X	X	X	X	X		
Comprehensive Serum Chemistry Panel	X	X	X	X	X	X	X	X	X		
Urinalysis ⁵				X			X			X ³	
T3, FT4, TSH ³				X			X			X ³	
Patient reported outcomes											
EORTC QLQ C-30	X		X		X		X		X	X ⁴	
EORTC QLQ-H&N35	X		X		X		X		X	X ⁴	
Efficacy Measurements											
Tumor Imaging ⁵			X ⁵		X ⁵		X ⁵		X ⁵	X ⁵	

1. Patients that develop a complete response during this phase of treatment will be followed as per table 6.2.
2. Patients will continue treatment with pembrolizumab for up to 24 months (from first dosage) or until progression of disease, complete response, discontinuation because of toxicity, or withdrawal from study.
3. Urinalysis and T3, FT4, TSH to be drawn before every 4th cycle (i.e. Cycle 18, Cycle 22, etc.).
4. EORTC QLQ C-30 and EORTC QLQ-H&N35 will be filled out by the patient every other cycle. The EORTC QLQ C-30 should be completed first.
5. Tumor imaging with CT neck and chest with IV contrast will be obtained after each 3rd cycle (or sooner if clinically indicated) Imaging should be reviewed to determine disease status prior to giving every 4th cycle . Definition of response is as per section 7.1.2.6.4. If the investigator feels that MRI will be the best way to follow the patient's head and neck disease subsequently, then an MRI of the neck should be done at baseline as well. However, CT scan is encouraged over MRI.
6. Vital signs to include temperature, pulse, respiratory rate, blood pressure, and oxygen saturation as measured by pulse oximeter.

6.4 Follow Up Phase for Patients with Progressive Disease or Who Discontinue Treatment Because of Toxicity or Any Other Reason (other than completing all eligible cycles of pembrolizumab treatment).

These patients will be taken off of pembrolizumab and enter the follow up phase.

Trial Phase	Safety Follow-up	Follow-up		Survival Follow-up ¹
Time from Last pembrolizumab Dose	30 days	3 months	6 months	Starting at 9 months
Visit	Safety Follow up visit	Follow up visit 1	Follow up visit 2	NA
Scheduling Window	+/- 3 days	+/- 7 days	+/- 7 days	+/- 7 days
Administrative Procedures				
Review Medications	X	X	X	
Subsequent Antineoplastic Therapy	X	X	X	X
Survival Status				X
Clinical Procedures/Assessments				
Review Adverse Events	X	X	X	
ECOG Performance Status	X	X	X	
Directed Physical Exam	X	X	X	
Vital Signs and Weight ³	X	X	X	
Laboratory Procedures/Assessments				

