7.1.2.6.4 Assessment of Disease

7.1.2.6.4.1 Definitions

Measurable Lesions: Lesions that can be accurately measured in at least one dimension with longest diameter at least ≥ 10 mm on CT scan (or >20 mm by X-ray). Cystic lesions thought to represent cystic metastasis can be considered as measurable lesions.

Malignant Lymph Nodes: To be considered pathologically enlarged and measurable, a lymph node must be ≥ 15 mm when assessed by CT scan.

Non-measurable Lesions: All other lesions < 10 mm or lymph nodes < 15 mm by CT scan.

Target Lesions: All measurable lesions up to a maximum of 2 lesions per organ and up to 5 lesions in total, representative of all involved organs, should be identified as target lesions and recorded and measured at baseline. Target lesions should be selected on the basis of their size (lesions with the longest diameter), be representative of all involved organs, but in addition should be those that lend themselves to reproducible repeated measurements. It may be the case that, on occasion, the largest lesion does not lend itself to reproducible measurement. In this circumstance, the next largest lesion which can be measured reproducibly should be selected. A sum of the diameters (longest for non-nodal lesions, short axis for nodal lesions) for all target lesions will be calculated and reported as the baseline sum diameters. If lymph nodes are to be included in the sum, then only the short axis is added into the sum. The baseline sum diameters will be used as reference to further characterize any objective tumor regression in the measurable dimension of the disease.

Non-target Lesions: All other lesions (or sites of disease) including any measurable lesions over and above the 5 target lesions should be identified as non-target lesions and should also be recorded at baseline. Measurements of these lesions are not required, but the presence, absence, or in rare cases unequivocal progression of each should be noted throughout follow-up.

7.1.2.6.4.2 Evaluation of Disease Response

Response determination will be defined based on RECIST 1.1. (Table 8).

Table 8. Definition of Response in Target Lesions.

Response	Definition
Complete Response (CR)	Disappearance of all target lesions*
Partial Response (PR)	At least a 30% decrease in the sum of the diameters of target lesions, taking as reference the baseline sum diameters

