Progressive Disease (PD)	At least a 20% increase in the sum of the diameters of target lesions compared to baseline sum of target lesions, or any new lesions
Stable Disease (SD)	Neither sufficient decrease to qualify as a PR or sufficient increase to qualify as PD

*After treatment of SCCHN patients with radiation it may be difficult to distinguish residual disease from treatment effect/normal tissue. This will be a critical consideration at 3 months post completion of radiation. As detailed above PET/CT can play a significant role in determination of residual disease at 3 months post completion of radiation. If a target lesion has decreased in size but has not completely resolved and the lesion is not PET avid (defined as an SUV that is not higher than background soft tissue) then the patient is considered to have a complete response. If a target lesion has decreased in size, but has not completely resolved, and it has any PET activity a biopsy can be done at the discretion of the investigator. If a biopsy done and is negative then the patient will be considered to have a complete response. If the biopsy shows residual malignancy or a biopsy is not done then the patient will be considered to have a partial response or stable disease as determined by RECIST 1.1.

Per RECIST 1.1, response should be confirmed by a repeat CT scan. The scan for confirmation of response may be performed at the earliest 4 weeks after imaging that showed response (if clinically indicated) or at the next scheduled scan.

Lesions that can be measured clinically on physical exam (skin lesions or palpable lymph nodes) will be measured by the investigator with the longest axis recorded. These measurements can be used to guide clinical decision making, for example prompting an earlier CT scan to evaluate disease. However, only measurements based on radiology will be used to determine response.

Table 9. Assessment of Non-Target Lesions

Response	Definition
Complete Response (CR)	Disappearance of all non-target lesions
Incomplete Response/Stable Disease (SD)	Persistence of one or more non-target lesions
Progressive Disease	Appearance of one or more new lesions and/or unequivocal progression of existing non-target lesions

Although a clear progression of “non-target” lesions only is exceptional, in such circumstances, the opinion of the treating physician should prevail.

7.1.2.6.4.3 Evaluation of Best Overall Response

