8.2.3 Efficacy

Endpoints Primary

Progression-free survival (PFS) – Progression free survival is defined as the time from the initiation of treatment to the first documented disease progression per RECIST 1.1 or death due to any cause, whichever occurs first. If a patient recurs and is eligible for retreatment, then only the time to the initial recurrence will be included in the evaluation of PFS. Patients who are alive with no evidence of disease at the time of last contact will be censored at that date.

Secondary

Overall Response Rate (ORR) – The overall response rate is defined as the percentage of the patients who have a complete response (CR) or partial response (PR) as defined by RECIST 1.1. The patient's best overall response rate defined as the best response recorded from the start of the treatment until disease progression will be recorded.

Clinical Benefit Rate (CBR) - Clinical benefit rate is the percentage of patients that have achieved a complete response, partial response, and stable disease as defined by RECIST 1.1.

Time to in-field progression – The time to in-field progression is defined as the time from initiation of treatment to progression of disease within the radiation field.

Overall Survival – Overall survival is defined as the time from first treatment until death. Patients who are alive will be censored at the last date of patient contact.

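### Table 8 measures target-lesion progression from the baseline sum, so regrowth after shrinkage is dated at the same scan or later, never earlier, and PFS can only lengthen

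*Combined protocol and SAP*

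**What the plan says.** Section 7.1.2.6.4.2 presents Table 8 as its statement of RECIST 1.1 response. The progression row reads "At least a 20% increase in the sum of the diameters of target lesions compared to baseline sum of target lesions", or any new lesion. Stable disease is the remainder: "Neither sufficient decrease to qualify as a PR or sufficient increase to qualify as PD". The definitions in 7.1.2.6.4.1 make the baseline sum the reference for tumor regression and name no reference for progression. The smallest on-study sum appears nowhere in the documents.

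Other sections send sites to this rule:

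- Section 6.1, footnote 9: "See section 7.1.2.6 for all details on definitions of response".
- Section 6.3, footnote 5, for patients in partial response or stable disease: "Definition of response is as per section 7.1.2.6.4".
- Section 5.9.1, among the reasons to stop treatment: "Confirmed radiographic disease progression. See Section 7.1.2.6".

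The primary endpoint in section 8.2.3 is time to "first documented disease progression per RECIST 1.1 or death due to any cause". That section and appendix 12.3 name RECIST 1.1 but do not restate its progression rule.

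**The concern.** Every patient has measurable disease and receives 60 Gy, so shrinkage followed by regrowth is a plausible way to fail. Under Table 8, such a patient without complete response is not called progressed on target lesions until the sum stands 20% above where it started, however far it fell in between.

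Three things are at stake.

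- **The primary endpoint.** Any effect on PFS goes one way. There is no concurrent arm in which the same lateness would cancel; the comparator is a fixed median of 8 months.
- **Treatment.** Section 6.3, footnote 2 says "Patients will continue treatment with pembrolizumab for up to 24 months (from first dosage) or until progression of disease", so a late call can keep a patient on pembrolizumab while the tumor regrows. Time to in-field progression faces the same delay.
- **Consistency.** The plan does not say whether Table 8 or the cited publication dates the event. If the two differ, two assessors could date the same patient differently, and both could claim to follow the protocol.

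**Working it through.** **1. The plan's own figure.** Section 8.2.2 gives 48 patients, a one-sided 5% test, medians of 8 and 12 months, and 78% power. Accrual is 24 months, with 12 months of further follow-up. With exponential PFS at a median of 12 (hazard 0.0578 per month), the event probability is 1 − (0.5 − 0.125)/(24 × 0.0578) = 0.73, or 35.0 events in 48 patients. Power = Φ(√35.0 × ln 1.5 − 1.645) = 77.5%. An exact chi-square test with 35 events gives 78.8%. The 78% reproduces and does not depend on the progression reference.

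**2. Direction.** The smallest sum is never above the baseline sum, so 1.2 × baseline is never below 1.2 × smallest sum. In 20,000 simulated shrink-then-regrow patients scanned at week 17 and every 9 weeks after, the baseline rule called progression later in 16,701, at the same scan in 3,299 and earlier in none.

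**3. Growth needed.** Set baseline to 100 and let f be the smallest sum as a fraction of baseline. Table 8 requires growth of 1.2/f − 1 from the smallest sum.

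| Shrinkage | Smallest-sum rule calls PD at | Table 8 calls PD at | Regrowth needed under Table 8 |
|---|---|---|---|
| 20% | 96 | 120 | 50% |
| 30% | 84 | 120 | 71% |
| 50% | 60 | 120 | 140% |

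**4. Delay (assumed growth rates).** The two thresholds differ by a factor 1/f, so the delay is ln(1/f)/g. Take diameters growing 20% per month (g = ln 1.2 = 0.182) to 20% per 9-week scan interval (63 days, 2.07 months).

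- 20% shrinkage: 0.223/0.182 = 1.2 months, up to 1.2 × 2.07 = 2.5 months.
- 30% shrinkage: 0.357/0.182 = 2.0 months, up to 4.0 months.

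Death or another form of progression can end PFS first. I assume a hazard of 0.2 per month for this (median 3.5 months). That lies within the 2 to 5 months separating the median PFS of 7–8 and median OS of 10–12 in section 4.2.1. The mean delay is then (1 − e^(−0.2d))/0.2: 1.1 to 2.0 months after 20% shrinkage and 1.6 to 2.8 after 30%.

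**5. Effect on the test.** Simulation of 100,000 trials per scenario: n = 48, true median 8, uniform accrual over 24 months plus 12 months. The test is a one-sample log-rank, (E − O)/√E > 1.645, which is assumed because the plan names none. Only events after the week-17 scan (119 days, month 3.9) may be delayed. At that time 0.5^(3.9/8) = 71% of patients, about 34 of 48, are event-free. Each delay is cut short by the competing hazard above.

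| Share of later events delayed | Patients | Maximum delay (months) | Median reads | False positives |
|---|---|---|---|---|
| None | 0 | – | 8.0 | 4.1% |
| 15% | about 5 | 2.0 | 8.3 | 5.2% |
| 15% | about 5 | 4.0 | 8.5 | 5.9% |
| 30% | about 10 | 2.0 | 8.5 | 6.4% |
| 30% | about 10 | 4.0 | 8.9 | 8.6% |
| 50% (upper bound) | about 17 | 4.0 | 9.5 | 13% |

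The same test has 79% power at a median of 12.

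**The case against.** **RECIST 1.1 is named.** The PFS definition, the confirmation rule and appendix 12.3 all cite it, and 7.1.2.6.4.1 ties the baseline sum to regression only. On that reading the progression row is a wording slip beside a named standard. This is fair as to intent, but it does not settle the matter. The documents never restate the cited progression rule or say that it overrides Table 8, and Table 8 is the only written threshold, to which sites are repeatedly sent.

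**The benchmark may carry the same lateness.** The false-positive rates treat 8 months as a median measured from the smallest sum. The cited reirradiation trials were published from 2001 to 2008, before the 2009 RECIST 1.1 paper, and their criteria are not given. If their rules were equally late, nothing is inflated. This stands: the rates show the effect of a difference in rules, not a demonstrated error rate.

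**The window opens too early.** Week 17 is the first scheduled scan after baseline, so regrowth from a sum recorded there needs a later scan, normally week 26 (month 6.0, 60% event-free at a median of 8). This also stands. With that start, false positives are 5.0–5.7% for a 15% share, 6.1–7.9% for 30%, and 11.5% at the upper bound. The effect is trimmed, not removed.

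**The exposed group is limited.** New lesions, unequivocal non-target progression and death still end PFS on time. A shrunken residual that is not PET-avid or is biopsy-negative counts as complete response, and recurrence after that is biopsied. The investigator may also withdraw a patient. All true, so only target-lesion regrowth in patients without complete response is affected.

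**An absolute minimum could reverse the order.** If the intended rule also required an increase of, say, 5 mm (an assumption), Table 8 would call progression earlier in 125 of the 20,000 simulated patients. These would be small tumors with little shrinkage.

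**Conclusion.** The concern holds. As written, Table 8 dates target-lesion regrowth in patients without complete response at the same scan or later than a 20% rule measured from the smallest sum. That direction is certain. The size is not: the shares delayed, growth rates, competing hazard and test are all assumed. Under the middle scenarios (15% to 30% of later events), the median moves by 0.3 to 0.9 months. The false-positive rate goes from 4.1% to 5.2–8.6%, or 5.0–7.9% if delays start at week 26. The extreme scenario gives 11.5% to 13%. Whether PFS is inflated against the historical 8 months cannot be established from the documents. It should be fixed because it is a one-directional risk to the primary endpoint of an uncontrolled trial. It does not undermine the sample size.

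**What to change.** In Table 8, define target-lesion progression as a sum of diameters at least 20% above the smallest sum recorded on study, counting baseline if it is the smallest. Keep any new lesion as progression, and add reappearance of a target lesion after complete response, subject to the biopsy in section 6.2. Leave baseline as the reference for partial response only. If a minimum absolute increase is wanted, state it in the same row. In section 8.2.3, point the PFS definition to this row so that one rule dates the event.

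The cost is one table row and one cross-reference, with no added scans. Median PFS may come out slightly shorter, and some patients would stop pembrolizumab earlier. If assessors already measure from the smallest sum, the edit only brings the text into line with practice.

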Patients that meet the eligibility criteria will undergo PET/CT for baseline imaging and will require tumor tissue for evaluation for PD-L1 expression. Fresh tissue or archival tissue will be obtained and used for PD-L1 analysis. PD-L1 expression will not be required for entry onto the study, given it is unknown if PD-L1 is predictive when pembrolizumab is combined with radiation, and given preclinical data suggesting that radiation leads to an increase in IFN- γ and subsequent PD-L1 expression in the tumor.¹ As highlighted in the study schema, patients will be treated with radiation (1.2Gy BID for total 60Gy) concurrent with pembrolizumab at 200mg intravenous every 3 weeks. The first dosage of pembrolizumab will be given on the first or second day of radiation. After completion of radiation treatment, patients will continue to receive pembrolizumab as a single agent for 3 months. At 3 months after completion of radiation, all patients will undergo a PET/CT to evaluate for response. Patients with a complete response (CR) at 3 months will discontinue pembrolizumab therapy and be observed with clinical exam and repeat CT neck at least every 3 months in the first year and every 6 months in year 2. These patients will then have continued annual follow-up with physical exam and CT neck (as clinically indicated) until the end of the study. Patients with a partial response or stable disease will continue treatment with pembrolizumab up to a total of 24 months (104 weeks) from the first cycle of treatment as long as they do not develop progressive disease, an intolerable toxicity, or other criteria for study withdrawal. These patients will be monitored with CT neck/chest after every 3rd cycle of pembrolizumab or more frequently if clinically indicated. Patients with progressive disease at 3 months post reirradiation will be taken off pembrolizumab and followed for survival. A patient who achieves a CR at 3 months post reirradiation and subsequently progresses may be eligible for retreatment with pembrolizumab as a single agent for up to one year. However, only the time to initial progression will be included in the PFS analysis, the primary endpoint of the study. Determination of response will be as per RECIST 1.1. However, given the experience with immune co-signaling blockade and the possibility of an inflammatory reaction leading to an increase in size of target lesions as well as the development of new lesions initially (before subsequent regression), progressive disease in the absence of clinical deterioration will be verified with repeat CT imaging not less than 4 weeks from prior imaging.^{2,3}

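### The Table 8 footnote tests one target lesion but classifies the whole patient, so a patient with discordant residual target lesions is CR by one sentence and PR/SD by another

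*Combined protocol and SAP*

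**What the plan says.** Table 8 (section 7.1.2.6.4.2) defines CR in target lesions as the loss of all of them. An asterisk on that entry leads to a footnote for the 3-month assessment, when residual tumour is hard to tell from treatment effect. The footnote has three operative sentences:

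- PET: "If a target lesion has decreased in size but has not completely resolved and the lesion is not PET avid", "then the patient is considered to have a complete response".
- Negative biopsy of a shrunken lesion with PET activity: "If a biopsy done and is negative then the patient will be considered to have a complete response".
- Positive biopsy, or none: if malignancy remains or "a biopsy is not done then the patient will be considered to have a partial response or stable disease as determined by RECIST 1.1".

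Other passages bear on how these apply:

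- Section 7.1.2.6.4.1 takes as target lesions "All measurable lesions up to a maximum of 2 lesions per organ and up to 5 lesions in total". All other disease is non-target. Inclusion criterion 9 sets a minimum of one measurable area, not a maximum.
- For non-target lesions, Table 9 defines CR as "Disappearance of all non-target lesions". It has no PET or biopsy exception.
- Table 10 (section 7.1.2.6.4.3) gives overall CR only for target CR, non-target CR and no new lesion. Target CR with persisting non-target disease is PR. Any new lesion is progressive disease (PD).
- Section 8.2.3 counts CR and PR in the overall response rate (ORR), and CR, PR and SD in the clinical benefit rate (CBR).
- Section 2.1 ties treatment to the category: "Patients with a complete response (CR) at 3 months will discontinue pembrolizumab therapy and be observed with clinical exam". Patients with PR or SD continue.

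**The concern.** The unit changes between condition and conclusion. The test is applied to a lesion and the result is given to the patient. With several residual target lesions, two footnote sentences can apply at once and give different answers. Nothing says that all lesions must qualify, or which sentence prevails.

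The footnote's conclusion also mentions neither non-target nor new lesions, so on its literal words it pre-empts Table 10.

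ORR and best overall response are listed secondary endpoints, and a patient who is SD by the sum of diameters could enter ORR through one non-avid lesion. The same label selects chart 6.2 or chart 6.3, and with it treatment and imaging, so two sites could handle identical findings differently.

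**Working it through.** The plan gives no figure on this point, so there is none to reproduce. The check applies each footnote sentence literally and compares the result with Tables 8 to 10.

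**1. When do the sentences collide?** Give each target lesion one of five states: gone; residual and non-avid; avid with negative biopsy; avid with positive biopsy; avid without biopsy. The second and third trigger CR; the fourth and fifth trigger PR/SD. Ignoring order, n lesions have C(n+4, 4) patterns. Those that trigger both answers number C(n+4, 4) − 2·C(n+2, 2) + 1.

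| Target lesions | Patterns | Both CR and PR/SD |
|---|---|---|
| 1 | 5 | 5 − 6 + 1 = 0 |
| 2 | 15 | 15 − 12 + 1 = 4 |
| 3 | 35 | 35 − 20 + 1 = 16 |
| 4 | 70 | 70 − 30 + 1 = 41 |
| 5 | 126 | 126 − 42 + 1 = 85 |

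These are counts of patterns, not frequencies of patients. Two lesions is probably the commonest multi-lesion case: three or more targets need at least two organs, and distant metastases are excluded.

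**2. Examples (lesion sizes assumed).**

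- Baseline 30 + 20 = 50 mm. Follow-up 28 mm (avid, no biopsy) + 10 mm (non-avid) = 38 mm. Change (38 − 50)/50 = −24%. This is SD by Table 8 and the last footnote sentence, but CR by the PET sentence.
- Baseline 50 mm as above. Follow-up 45 + 16 = 61 mm, with the 16 mm lesion non-avid. Change (61 − 50)/50 = +22%. This is PD by Table 8 (subject to confirmation), but CR by the PET sentence applied to the smaller lesion.
- Non-avid residual target with a persisting non-target lesion: CR by the footnote's words, PR by Table 10. With a new lesion instead: CR by the footnote's words, PD by Table 10.

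**3. Which results move?** SD versus CR changes ORR by 1/48 = 2.1 points per patient. PR versus CR changes the CR count but not ORR. CBR does not change among CR, PR and SD.

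**4. How many patients?** The documents give neither the number of lesions per patient nor PET agreement between lesions, so these inputs are assumptions: each residual lesion is PET-negative with probability 0.3 to 0.7; two lesions per patient have latent-normal correlation 0.3 to 0.9; 25% to 50% of 48 patients (12 to 24) have more than one residual target lesion; and no avid lesion is rescued by a negative biopsy. The gap is the probability that any lesion is non-avid minus the probability that all are.

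| Correlation | Gap |
|---|---|
| 0.3 | 0.34 to 0.40 |
| 0.6 | 0.25 to 0.30 |
| 0.9 | 0.12 to 0.14 |

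As a check, at probability 0.5 the gap is arccos(correlation)/π: 0.40, 0.30 and 0.14.

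Low end: 12 × 0.12 = 1.4 patients (1.4/48 = 3%). High end: 24 × 0.40 = 9.6 patients (9.6/48 = 20%). These are changes between CR and PR/SD; only those who would otherwise be SD alter ORR.

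**The case against.** The best defence is the position of the asterisk. It sits on the target-lesion CR entry, in a table confined to target lesions, within a section governed by RECIST 1.1. Read that way, the footnote only says when a residual lesion counts as gone: the requirement for all target lesions stays in force, and Table 10 still combines the parts. That is probably the intent. A reader might infer that the plan deliberately overrides Tables 9 and 10; the documents do not support that, and this part is a fault of wording. It remains a fault, because the footnote names the patient in each result and never refers to Table 10.

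Three further inferences go too far.

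- **CR rate as an endpoint.** It is not listed as a secondary endpoint in sections 2.1, 3.2 or 8.2.3. A large swing in CR count is not an equal swing in ORR.
- **A firm size.** The range rests wholly on assumed inputs. Leaving out high correlation would overstate the minimum, and 12 to 24 patients makes no allowance for progression, death or full resolution before the 3-month PET/CT.
- **Harm to the primary endpoint.** Charts 6.2 and 6.3 differ by design: neck CT every 3 months (about 13 weeks) in the first year, against neck and chest CT after every third 3-week cycle (9 weeks). The footnote affects progression-free survival (PFS) mainly indirectly, by deciding who follows which chart. A direct effect needs its literal CR to coincide with PD by Table 8 or Table 10.

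Footnote 9 of chart 6.1 requires confirmation and keeps patients on pembrolizumab meanwhile, so one reading does not act at once. But confirmation is by CT, which cannot settle a status based on PET or biopsy.

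**Conclusion.** The point stands as a defect in a response definition. For patients with two or more residual target lesions whose PET or biopsy results differ, the footnote gives both CR and PR/SD, against Table 8's own requirement. Its silence on Table 10 is a second, lesser ambiguity. There is no problem for a patient with a single target lesion, or whose lesions agree, provided no non-target lesion persists and no new lesion appears.

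The firm figure is 2.1 ORR points for each patient moved between SD and CR. The estimate of roughly 1 to 10 patients changing category depends on the assumptions in the working and could be smaller. CBR is unaffected among CR, PR and SD. The documents do not support a claim that the PFS analysis is materially biased by this wording. The ambiguity should be removed before responses are scored.

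**What to change.** Reword the footnote at lesion level. Target-lesion CR by PET or biopsy should require every residual target lesion to meet the footnote's existing shrinkage condition and to be either non-avid or biopsy-negative. If any avid residual target lesion is unbiopsied or biopsy-positive, the result is PR or SD by RECIST 1.1, as the last footnote sentence already has it. Then state that overall response is read from Table 10.

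The sponsor should also reconcile whether the PET/biopsy exception covers non-target lesions in Table 9. That is a design choice: relative to Tables 9 and 10 as written it could raise the CR count, and section 7.1.2.6.4.1 does not require non-target lesions to be measured, so a shrinkage condition for them would need thought.

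Because CR also decides the treatment path, section 2.1, footnote 9 of chart 6.1, section 7.1.4.1 and section 7.1.5.2.1 must refer to the one reconciled definition. This review takes no position on which path any patient should follow.

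The target-lesion change costs only protocol wording and uses the same PET/CT and the same optional biopsy. The downside is that the reported CR count may change slightly, in either direction depending on how non-target lesions are handled.
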